## 5 Number of Participants

Indicate the total number of participants to be recruited and enrolled: 20

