**Part B (weeks 5-9):**

Participants will be randomized to either receive or not to receive prompts every work hour (8 per day) via email, for 4 weeks. A total of 80 prompts will be sent to participants over a 4-week period during their work hours (9AM-5PM) on workdays.

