### *PART B*

For instances where prompts were sent and a response occurred, the response time will be recorded (seconds) and the average response time calculated. The number of responses occurring each hour will be calculated to identify the frequency of responses by hour. Generalized estimating equations (GEEs) will be ran using GENMOD (with a repeated statement) to examine the main effect of prompt delivery (sent or not sent) by modeling the mean likelihood of a response as an odds ratio, over the next 5-minute and 30-minute periods. An autoregressive model will be used to account for time dependency and the correlation between observations. Mixed model analyses will be conducted using PROC MIXED to examine the association between prompt type and total sedentary time over the next 5-minute and 30-minute period. All models will be adjusted for age, race, gender, day of intervention and minutes of sitting 30 minutes prior to a prompt. Decision points where the participant was standing or moving at the time of prompt delivery (sent) or scheduled (not sent) time will be excluded from analyses.

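### The autoregressive working correlation in the Part B GEE can bias the acute prompt odds ratio if a prompt carries over to the next hour; working independence avoids this at little cost

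*SAP*

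**What the plan says.** The Protocol (section 7, Part B) states: "Participants will be randomized to either receive or not to receive prompts every work hour (8 per day) via email, for 4 weeks". Aim 2 calls the design micro-randomised, and the SAP refers to decision points at which a prompt was scheduled but not sent. I therefore read prompt status as varying from hour to hour within a participant. The Protocol adds: "A total of 80 prompts will be sent to participants over a 4-week period". Section 5 sets the sample at 20 participants.

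The SAP (Statistical analyses, PART B) plans a GEE for the main effect of prompt delivery, "modeling the mean likelihood of a response as an odds ratio, over the next 5-minute and 30-minute periods". On dependence it says only: "An autoregressive model will be used to account for time dependency and the correlation between observations". The covariates are age, race, gender, "day of intervention and minutes of sitting 30 minutes prior to a prompt". Decision points at which the participant was already standing or moving are dropped.

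The SAP has no previous-prompt term and does not assume that earlier prompts leave later responses unchanged. It does not state the cluster (participant or participant-day), the time ordering within cluster, or the type of standard error. Aim 2 makes the change from sitting to standing within 5 minutes the primary outcome, which I take to be the response in the 5-minute model.

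**The concern.** A GEE with a non-diagonal working correlation estimates the intended contrast only if the mean response at one hour does not also depend on covariates from other hours that are missing from the model. With prompts re-randomised hourly and only the current prompt in the model, that condition fails if a prompt at one hour directly alters the response at the next. The autoregressive weights then multiply this hour's prompt by the next hour's residual, so carry-over enters the acute estimate with its sign reversed when rho is positive. Empirical standard errors do not repair this, because the point estimate itself moves. The estimate affected is the main effect of prompt delivery on the primary outcome.

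**Working it through.** **Inputs from the documents.** 8 decision points a day x 20 workdays = 160 per participant. 80 prompts / 160 = 0.5, the implied prompt probability (derived, not stated). There are 20 clusters. The documents give no response rate, odds ratio, power, rho or carry-over, so there is no figure of the plan's to reproduce. Everything below on rho and carry-over is assumed.

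**Algebra (identity link, prompts independent between hours).** Let A be the centred prompt with variance v, b the acute effect, and g the effect of the previous prompt on the current response. Interior rows of the inverse AR(1) matrix are proportional to (-rho, 1+rho², -rho). At the limiting estimate b*, with residual e, the expected estimating equation for the prompt is

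(1+rho²)·E[A_t e_t] - rho·E[A_t e_(t+1)] - rho·E[A_t e_(t-1)] = 0.

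The three expectations are (b - b*)v, g·v and 0. Hence b* = b - rho·g/(1+rho²). The multiplier of g is -0.10, -0.19 and -0.28 at rho = 0.1, 0.2 and 0.3. For example, rho = 0.1 and g = -0.6 give 0.6 x 0.099 = +0.06. Working independence sets the off-diagonal weights to zero, so b* = b.

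**Logistic scale, limiting values.** Simulation with 12,000 participants, 160 points each, prompt probability 0.5, baseline logit -1.4 and acute log odds ratio 0.6 given the participant. The fitted odds ratios are population-averaged. SD is that of the participant intercept.

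| Carry-over (log odds) | SD | Fitted rho | OR, independence | OR, AR(1) | Shift in log OR |
|---|---|---|---|---|---|
| None | 0.8 | 0.105 | 1.708 | 1.709 | 0.000 |
| Direct, -0.3 | 0.8 | 0.099 | 1.707 | 1.746 | +0.023 |
| Direct, -0.6 | 0.5 | 0.040 | 1.769 | 1.804 | +0.020 |
| Direct, -0.6 | 0.8 | 0.093 | 1.701 | 1.775 | +0.043 |
| Direct, -0.6 | 1.2 | 0.185 | 1.619 | 1.744 | +0.075 |
| Direct, +0.6 | 0.8 | 0.113 | 1.683 | 1.597 | -0.052 |
| Through own standing, -0.6 | 0.8 | -0.001 | 1.723 | 1.723 | 0.000 |
| Through own standing, -1.5 | 0.5 | -0.141 | 1.755 | 1.733 | -0.013 |
| Only through the prior-sitting covariate | 0.8 | 0.096 | 1.716 | 1.716 | 0.000 |

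The logistic shifts are smaller than the linear formula but follow its sign. At g = -0.6 and rho = 0.093 the formula gives 0.6 x 0.093/1.0086 = 0.055, against 0.043 simulated.

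A second set of assumptions (acute log odds ratio 0.7, 75% of points seated, SD 0.5 to 1.2, hourly latent serial correlation 0.5 to 0.8) gave fitted rho of 0.03 to 0.25. The shifts were +0.01 to +0.03 at carry-over -0.3, +0.01 to +0.07 at -0.6, and -0.01 to -0.035 at +0.3.

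**Against the standard error.** With 20 participants the standard error is about 0.08 to 0.13. The largest shift in the table, 0.075, compares with a mean standard error of 0.084 in the same setting: 0.075/0.084 = 0.89.

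**Coverage with 20 participants (1,000 replicates, first set of assumptions).**

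| Direct carry-over, SD | 95% coverage (z), AR(1) | 95% coverage (z), independence |
|---|---|---|
| None, 0.8 | 92.4% | 91.9% |
| -0.6, 0.8 | 89.3% | 91.3% |
| -0.6, 1.2 | 83.4% | 92.5% |

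Over the five settings simulated, independence covered 91% to 93% with z and 93% to 95% with t on 19 degrees of freedom. Its limiting odds ratio equalled the crude sent versus not-sent odds ratio in all five.

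**The case against.** **A reader might infer that the autoregressive fit overstates the effect whenever prompts merely bring forward a stand that was coming anyway.** That does not follow. Displacement of that kind works through the participant's own standing, which also pulls rho towards or below zero. Shifts under that mechanism ran from -0.015 to +0.006 across all settings tried. A material shift needs the prompt itself to alter the next hour's response, for example through annoyance (negative) or a lasting reminder (positive). The documents neither describe nor exclude such a pathway.

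**A reader might also infer an inflated false-positive rate.** That requires a prompt with no acute effect that still changes the next hour. A prompt that triggers no stand brings none forward, and with no acute effect and own-standing displacement the bias was 0.0001. Another pathway would be needed, such as standing after the 5-minute window, and the documents name none.

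**The plan already adjusts for prior sitting.** Carry-over that runs wholly through that covariate causes no bias. This stands, but the covariate covers only the 30 minutes before an hourly decision point, so it need not capture everything.

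**Misdated lags depend on coding.** If rows are taken in order within participant, 19 of 159 adjacent pairs (16 overnight, 3 weekend) would be treated as one-hour lags before any exclusions. With the participant-day as cluster there are none. The SAP does not say which applies, so this is a gap in specification and not a demonstrated error.

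**The studies are described as exploratory and the bias is under one standard error.** Both are true, and they limit the weight of the point. They do not favour the autoregressive choice, which gains little precision and rests on an unstated assumption of no carry-over.

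**Conclusion.** The concern holds in a limited form. With hourly randomised prompts and no previous-prompt term, the autoregressive GEE can bias the acute odds ratio if there is direct carry-over outside the prior-sitting covariate. The sign is that of -rho times the carry-over. Under the assumed rho of 0.1 to 0.25 and carry-over of -0.6 to +0.3, the shift is about -0.03 to +0.07 in log odds ratio, below one standard error at 20 participants. A stronger positive carry-over of +0.6 gave -0.05. With no carry-over the two structures agree. Neither rho nor carry-over is in the documents, so neither the direction nor the size of any bias in this trial can be fixed from them.

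The result also assumes that prompts are independent between hours. The Protocol gives the total of 80 but not how it is reached. Drawing 80 of 160 at random gives a correlation of -1/159 = -0.006 between any two hours' prompts, which is negligible. Fixing 4 of 8 each day would give -1/7 = -0.14 within a day, and carry-over would then reach the independence estimate as well.

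**What to change.** - Make working independence (TYPE=IND) the primary structure for the Part B GEE, with the participant as cluster.
- Use empirical standard errors with a small-sample correction or a t reference, since uncorrected z intervals fall short with 20 clusters whichever structure is used.
- Keep the autoregressive fit as a sensitivity analysis, with lags defined by clock hour within participant-day so that nights, weekends and dropped points do not count as one-hour lags.
- Optionally, add a previous-prompt term in a further sensitivity analysis so that carry-over is reported, and state how the 80 prompts are allocated.

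The cost is one option in the REPEATED statement and a few SAP sentences. The standard error may be up to about 5% larger when serial correlation is strong and there is no carry-over. In one 20-participant setting (direct carry-over -0.6, SD 1.2) the spread of estimates was 9% larger under independence (0.0886 against 0.0811), although the mean standard errors were almost equal. Even there the total error was smaller. The autoregressive bias was ln(1.747/1.62) = 0.0755, so its root mean square error was √(0.0811² + 0.0755²) = 0.111. Under independence the bias was ln(1.629/1.62) = 0.0055 and the root mean square error √(0.0886² + 0.0055²) = 0.089.

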**2 Background and Objectives**

Provide the scientific or scholarly background for, rationale for, and significance of the research based on the existing literature and how will it add to existing knowledge.

- Describe the purpose of the study.
- Describe any relevant preliminary data or case studies.
- Describe any past studies that are in conjunction to this study.

The unique attributes of sedentary behavior (SB) (e.g., ubiquitous, habitual, socially-reinforced) and its link to cardiometabolic health risk have led to several studies aimed at understanding the correlates of SB. However, these studies have primarily focused on "static" correlates (e.g., built environment, income status, educational attainment, etc.) and have largely ignored the complex situational, contextual, and dynamic "in the moment" factors that can influence SB.

The development of smart phone apps and wearable devices (e.g. Fitbit, apple watch, jawbone, etc.) within the technology industry has resulted in an increase in personal notifications to stand or move more during the workday. These prompts may vary in medium (phone, email, watch), delivery (textual, visual, sound, vibration) and content (personalized, generic, short, long, motivational, educational, feedback). However, the extent to which these prompts actually reduce SB is not fully understood.

The overall objective of this set of exploratory studies is to understand the personal, behavioral, environmental, and contextual factors that underpin SB and to systematically test a series of contextual prompt characteristics that may lead to subsequent change in SB.

The primary aims are:

**Aim 1.** Using Ecological Momentary Assessment (EMA), we will determine which personal (e.g. fatigue, mood, and stress level), behavioral (e.g. watching TV, working at desk, and eating meals), environmental (e.g. being at home or work, time of the day, and weather) and contextual factors are associated with SB. We will identify the combination of factors most likely to precede and proceed short (<30 min) and long (≥30 min) bouts of SB.

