**SOCIAL BEHAVIORAL INSTRUCTIONS AND TEMPLATE**

NUMBER	DATE	PAGE
HRP-503a	12/21/2017	3 of 6

This 10-week study has 2 main parts: (A) an EMA study and (B) a Screening experiment. Twenty participants will be recruited for the study.

Prior to the start of the study, participants will first have to complete an initial online screening survey to determine eligibility. All eligible participants will be requested to complete an online consent and depending on their smartphone operating system, will be sent instructions (see appendix D, E, F, and G) on how to download the smartphone apps that will be used in the study:

Smartphone App	OS	Description
PACO	Android or iOS	An open-source app designed that will be used to deliver EMA questions randomly throughout a participant's workday.
Daynamica	Android	An app designed to collect user activity and travel data using raw smartphone accelerometer and GOS data.
Prox	iOS	An iOS app designed to capture real-time indoor (office) location through proximity sensors deployed around the workplace.

Eligible and consented participants will be invited to a one-hour orientation session where they will be given detailed information about the study, along with answering any questions or concerns they may have. During this visit, proximity sensors will also be deployed to various key areas in the workplace (i.e., participant's desk, lobby, kitchen, and conference rooms).

Timeline:

	Week									
	Part A				Part B					
Measures	1	2	3	4	5	6	7	8	9	10
Main Survey	X						X			X
Daily logs	X	X	X	X			X	X	X	X
EMA	X	X	X	X						
Prompts							X	X	X	X
ActivPAL	X	X	X	X			X	X	X	X

Throughout Parts A and B (weeks 1-10):

All participants in both part A and B will be asked to complete daily logs that will ask them of the time they went to work and got off of work the previous day, sleep time of the previous night and the time they woke up, and any work-related meetings that they had the previous day. In addition, they will be asked to complete a battery of assessment (see appendix A for list of questionnaires) at three time points in the study: at week 1, 7, and 10. Participants will also be asked to wear the activPAL device on their thigh as an objective measure of sedentary and physical activities. They will be asked to wear the device continuously throughout the study except for the interview weeks (week 5 and 6). The activPAL will be dropped off every Monday morning and picked up every Friday of the same week.

Part A (Weeks 1-4):

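### The Part B models leave out the scheduled hour of each decision point, a pre-randomization variable that is free to add and could modestly improve efficiency

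*SAP*

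**What the plan says.** **Covariates.** SAP, Statistical analyses, PART B: "All models will be adjusted for age, race, gender, day of intervention and minutes of sitting 30 minutes prior to a prompt". This covers both the GEE for sent versus not sent and the mixed model for prompt type. The list has no hour or time-of-day term.

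**Hour elsewhere in the SAP.** It appears once, in a descriptive step: "The number of responses occurring each hour will be calculated to identify the frequency of responses by hour".

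**Time dependence.** The same section says: "An autoregressive model will be used to account for time dependency and the correlation between observations".

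**Decision points.** Protocol section 7, Part B: "Participants will be randomized to either receive or not to receive prompts every work hour (8 per day) via email, for 4 weeks". It adds: "A total of 80 prompts will be sent to participants over a 4-week period during their work hours (9AM-5PM) on workdays".

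**Time of day as a factor.** Protocol section 2, Aim 1, lists among the candidate determinants of sedentary behavior: "environmental (e.g. being at home or work, time of the day, and weather".

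**The concern.** Whether a seated person gets up in the next 5 or 30 minutes plausibly depends on the hour, whatever the prompt does: lunch and the end of the day are the obvious cases. Nothing already in the models clearly stands in for that pattern.

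- Day of intervention takes one value for all eight decision points of a day.
- Age, race and gender do not change within a person, so they explain none of the variation between one person's decision points, which is where the prompt contrast is made.
- An autoregressive structure describes correlation between neighbouring observations. It does not fit a mean that differs systematically from hour to hour.
- Prior sitting, together with the restriction to seated decision points, may absorb part of the pattern. A person seated at noon can still differ from one seated at 10AM with the same prior sitting.

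What is at stake is efficiency in a study of 20 people. There is also a smaller gain in discipline: if hour is specified now, nobody has to decide about it after seeing the hourly tabulation.

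**Working it through.** The documents give no power or precision figure for Part B, so there is none to reproduce. Every size below rests on an assumed hour effect.

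**1. Number of decision points.** Inputs: 8 per day and 4 weeks (Protocol section 7, Part B); 20 participants (Protocol section 5); 20 workdays in 4 weeks, the count that the protocol itself uses for Part A (3 × 20 × 20 = 1,200 EMAs).
- Per participant: 8 × 20 = 160.
- In total: 160 × 20 = 3,200 before the seated-only exclusion.
- If the 80 prompts are per participant, 80/160 = 0.5 of points are sent, at most 80 × 20 = 1,600 in all. This fits a constant probability of one half, but the protocol states no probability.
- Hour as a class variable: 8 − 1 = 7 degrees of freedom.

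**2. Mixed model (prompt type, sedentary minutes).** Let R² be the share of the variance left after the planned covariates that hour explains. With about 6 mean parameters before and 13 after,

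SE ratio = √[(1 − R²)(N − 6)/(N − 13)].

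| Assumed R² | SE ratio, N = 3,200 | SE ratio, N = 1,600 | Equivalent extra observations, 1/(1 − R²) − 1 |
|---|---|---|---|
| 1% | 0.996 | 0.997 | 1% |
| 2% | 0.991 | 0.992 | 2% |
| 5% | 0.976 | 0.977 | 5% |
| 10% | 0.950 | 0.951 | 11% |

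The column for 1,600 applies if prompt type is compared among sent prompts only, which the SAP does not settle. The result hardly depends on N.

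**3. Logistic GEE (sent versus not sent).** 500 simulated data sets per row: 20 people × 160 points, 60% kept as seated, conditional log odds ratio 0.4, intercept −1.4, person SD 0.5 on the logit scale, send probability 0.5, a linear hour trend with the SD shown, and person-clustered robust standard errors. The simulation used working independence in place of the autoregressive structure and left out the other SAP covariates.

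| SD of hour effect (logit) | Mean log OR without → with hour | Empirical SD of log OR | Mean z |
|---|---|---|---|
| 0.2 | 0.377 → 0.380 | 0.1073 → 0.1088 | 3.64 → 3.64 |
| 0.5 | 0.365 → 0.382 | 0.1105 → 0.1132 | 3.61 → 3.68 |
| 0.8 | 0.338 → 0.378 | 0.1043 → 0.1093 | 3.39 → 3.58 |

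In the last row the odds ratio moves from exp(0.338) = 1.40 to exp(0.378) = 1.46, its SD rises by 0.1093/0.1043 − 1 = 5%, and mean z rises by 3.584/3.388 − 1 = 6%.

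Peaked profiles give similar answers. With 5-minute response of 10–15% in most hours and 30–35% at noon and 4PM, or 12% against 40–45%, or 15–18% against 25–30% (87.5% seated, person SD 0.4), mean z went from 4.06 to 4.20, 3.91 to 4.09 and 4.40 to 4.43. These are rises of 3%, 5% and 1%. A repeat with other profiles in the same ranges raised squared z by 14% at the steepest, so z by √1.14 − 1 = 7%.

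**The case against.** The strongest reply is that this is an optional covariate in a study that calls itself exploratory, with a small and unknowable gain. Most of that stands. No document supplies an hourly profile, and prior sitting plus the seated-only restriction may already take up part of it. Four stronger readings are tempting, and the documents support none of them.

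- **That the prompt effect is biased.** If the send probability is the same at every hour, hour is independent of treatment and leaving it out does not confound the contrast. The documents do not state the probability, so bias can be neither asserted nor formally excluded.
- **That chance imbalance by hour is a separate harm.** With unrestricted 50:50 draws (an assumption), sends in one person-hour have SD √(20 × 0.25) = 2.2 around 10 of 20. The GEE estimates a pooled effect, however. Over 20 people the SD is √(400 × 0.25) = 10 around 200 of 400 sends, or 2.5 percentage points. The standard error already reflects such random imbalance.
- **That the omission widens the interval for the odds ratio.** This is linear-model reasoning. In the logistic GEE the omission mainly pulls the odds ratio toward 1, and adding hour slightly raises the standard error of the log odds ratio.
- **That the SAP expects an hour effect.** It plans a count of responses by hour and states no expectation. Aim 1 is better support, but it concerns determinants of sedentary behavior in Part A and is not a prediction about prompts.

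Larger gains can be produced by assuming a steep profile. A drop from 25 to 17 sedentary minutes in two of eight hours, with SD 8, gives between-hour variance 0.25 × 0.75 × 8² = 12 and R² = 12/(64 + 12) = 16%. Nothing in the documents supports that profile, and the calculation ignores the prior-sitting covariate.

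The reply does not remove the point that the variable is pre-randomization, already held and almost costless.

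**Conclusion.** The point holds as a modest, free improvement. Hour is absent from both Part B models although it is known before every randomization, and neither day of intervention nor the autoregressive structure represents an hourly mean.

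- **Mixed model:** about 0.4% to 5% lower standard error for the prompt-type contrast, if hour explains 1% to 10% of residual variance.
- **Logistic GEE:** an odds ratio further from 1 with a slightly larger standard error. Mean z is unchanged to about 6% higher for hour effects with SD 0.2 to 0.8 on the logit scale.

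Both ranges rest on assumed hour effects, and the GEE range also on a simplified model. If the send probability is constant over hours, this is efficiency only and the planned analysis is not biased by the omission.

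**What to change.** In SAP PART B, add the scheduled hour of the decision point as an 8-level class variable to the GEE and to the PROC MIXED model, for both the 5-minute and the 30-minute windows, beside day of intervention and prior sitting. Use the scheduled hour at sent and not-sent points alike, so that the covariate stays pre-randomization.

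State that the odds ratio for prompt delivery is then conditional on hour, since this changes the estimated quantity from one averaged over hours. State also whether the send probability is constant across hours, so that a reader can see that the adjustment serves efficiency.

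Cost: an added covariate and two sentences in the SAP, 7 degrees of freedom against at most 3,200 decision points before the seated-only exclusion, and no new data.

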**Aim 2.** Using a micro-randomized screening experiment, we will identify efficacious behavioral strategies to produce an acute (within 5 min of receiving the prompt) reduction in SB based on three factors: (a) behavioral target (sit-to-stand vs. sit-to-light physical activities (LPA)); (b) social effects (group vs. individual); and (c) content (Target set vs. No target set). Our primary outcome will be a change from a sitting behavior to a standing behavior within 5 minutes of receiving the prompts. Furthermore, we will look at overall stand time (minutes), steps.

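### Part B leaves out each participant's own Part A sit-to-stand rate as a covariate; adding it would bias nothing and would bring a small gain in test sensitivity at almost no cost

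*SAP*

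**What the plan says.** The primary outcome (Protocol section 2, Aim 2) is a "change from a sitting behavior to a standing behavior within 5 minutes of receiving the prompts". The SAP, PART B, fits a GEE with an autoregressive correlation structure "to examine the main effect of prompt delivery (sent or not sent) by modeling the mean likelihood of a response as an odds ratio", over 5 and 30 minutes. It fits a mixed model for sedentary time by prompt type. The covariates are the same throughout: "All models will be adjusted for age, race, gender, day of intervention and minutes of sitting 30 minutes prior to a prompt". Only decision points at which the participant was seated are analysed.

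Protocol section 7 says of the activPAL: "They will be asked to wear the device continuously throughout the study except for the interview weeks (week 5 and 6". Its timeline table shows the device in weeks 1-4 and again in weeks 7-10, with prompts in weeks 7-10. A four-week record without movement prompts therefore precedes the experiment for the same people.

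On the unit of randomization, Aim 2 reads: "Using a micro-randomized screening experiment, we will identify efficacious behavioral strategies". Protocol section 7, Part B, reads: "Participants will be randomized to either receive or not to receive prompts every work hour (8 per day) via email, for 4 weeks".

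**The concern.** In a contrast randomized within person, a covariate that is fixed for each person cannot correct bias. It can help only by predicting the outcome. Age, race and gender are likely to predict weakly who gets up often, particularly in 20 people. A participant's own measured rate of leaving sitting should do better, is fixed before randomization, and comes from data already planned. An autoregressive correlation fades with lag, so it does not represent a stable difference between people.

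At stake is a little sensitivity of the sent versus not-sent test, and a clear statement of which odds ratio is being estimated. Validity is not in question.

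**Working it through.** The plan states no event rate, effect size, between-person spread, alpha or power, so there is no planned figure to reproduce.

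**Inputs from the documents**
- Participants (Protocol section 5): "Indicate the total number of participants to be recruited and enrolled: 20".
- Decision points: 8 per day x 20 workdays = 160 per person; 160 x 20 = 3,200 before the seated-only exclusion.
- Allocation (Protocol section 7, Part B): "A total of 80 prompts will be sent to participants over a 4-week period". Read per person, 80/160 = 0.50, which fits about 1:1. The documents do not say whether 80 is fixed for each person or is an expected number.

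**Assumed inputs**
- 70% of points seated.
- Unprompted 5-minute standing probability 0.20.
- Conditional odds ratio 1.35.
- Two-sided alpha 0.05.
- Correlation 0.8 between a person's Part A and Part B tendencies.
- Person SD 0.3 to 1.2 on the logit scale.

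**Check.** Data were simulated 500 times per setting. Each data set was analysed by logistic GEE with AR(1) correlation and participant-clustered sandwich SE, first with the SAP covariates and then with the Part A log-odds added. Here z = mean log OR / empirical SD, and gain = (z after / z before)^2.

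| Person SD | Allocation | OR | Mean SE of log OR | z | Gain | Power |
|---|---|---|---|---|---|---|
| 0.3 | 80/80 | 1.357 to 1.360 | 0.0969 to 0.0975 | 3.18 to 3.18 | 1.00 | 0.872 to 0.872 |
| 0.3 | independent | 1.333 to 1.335 | 0.0974 to 0.0978 | 2.65 to 2.64 | 0.99 | 0.808 to 0.808 |
| 0.5 | 80/80 | 1.331 to 1.338 | 0.0953 to 0.0968 | 2.80 to 2.83 | 1.02 | 0.836 to 0.838 |
| 0.5 | independent | 1.342 to 1.348 | 0.0969 to 0.0980 | 2.87 to 2.89 | 1.01 | 0.830 to 0.830 |
| 0.8 | 80/80 | 1.318 to 1.335 | 0.0922 to 0.0954 | 2.73 to 2.77 | 1.03 | 0.830 to 0.846 |
| 0.8 | independent | 1.313 to 1.331 | 0.0948 to 0.0979 | 2.80 to 2.82 | 1.01 | 0.806 to 0.816 |
| 1.2 | 80/80 | 1.282 to 1.317 | 0.0900 to 0.0974 | 2.70 to 2.81 | 1.08 | 0.762 to 0.776 |
| 1.2 | independent | 1.295 to 1.326 | 0.0933 to 0.0998 | 2.61 to 2.73 | 1.09 | 0.788 to 0.792 |

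A larger simulation of the same model form (1,500 runs per setting, also on assumed inputs) gave gains of about 1%, 3-4% and 7% at person SD 0.3, 0.6 and 0.9 with independent allocation. With exact 80/80 the gain was about 0-3%. At the larger spreads its Monte Carlo intervals for the gain ratio lay above 1.

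**Where the gain comes from.** Take SD 0.8 with 80/80. The log OR goes from ln 1.318 = 0.276 to ln 1.335 = 0.289, a factor of 1.046. The empirical SD goes from 0.1009 to 0.1042, a factor of 1.033. The ratio is 1.046/1.033 = 1.013, and its square is 1.03. Both terms grow, and the estimate grows slightly more. This is the usual non-collapsibility of the odds ratio: conditioning on a person-level predictor moves it from marginal toward person-specific.

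**30-minute window.** A simpler logistic check used an assumed 60% event rate, 85% seated and correlation 0.9. It gave 3%, 6% and 16% at SD 0.3, 0.6 and 0.9 with independent allocation, and 0-5% with 80/80. It left out prior sitting, which favours the baseline, so these figures are on the generous side.

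**Caveat.** In several settings the mean sandwich SE is below the empirical SD (0.0922 against 0.1009 at SD 0.8, 80/80). The power levels are therefore somewhat optimistic, and only the before-and-after differences should be read.

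**The case against.** The strongest objection is that the Part A rate is itself constant within a person. It affects that person's sent and not-sent hours alike and largely cancels, just as age, race and gender do. This stands, and it is why the gain is small. Balance within person is not guaranteed, however, because the allocation rule is not stated and the seated-only exclusion would disturb an exact 80/80.

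A reader might infer that avoidable person-to-person noise remains in the odds ratio and that the covariate would remove it. The calculation does not support this, since the SE rose in every setting. A reader might also convert the gain into decision points saved, for instance about 250 of 2,800 seated points (250/2,800 = 9%, with 87.5% assumed seated). That takes the top of an assumed range, and the ratio used rises partly because the estimate itself changes meaning.

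It would also be wrong to read the demographic adjustment as an error. The SAP does not say it is there to control confounding, and it does no harm.

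Three further objections stand in part:
- Prior 30-minute sitting may already carry some of a person's tendency. It is in the GEE simulations, with only a weak person signal.
- Part A is not free of interruption: participants receive three random EMA signals per workday, and weeks 5-6 separate the two periods. The documents give no Part A to Part B correlation.
- The not-sent hours already give a concurrent unprompted rate, although the SAP's GEE does not include participant terms that would use it.

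**Conclusion.** The omission is real, and correcting it is an optional efficiency refinement. For person SD 0.3-0.9 on the logit scale, the gain in (estimate/SD)^2 is about 0-3% with balance within person and about 1-7% with independent allocation. Power rises by 0-2 points. At the more extreme SD of 1.2, the 500-run check gave 8-9%, still within 2 points of power. If the prompt effect itself varies between people (SD 0.4, with person SD 0.8), power goes from 0.666 to 0.684; the baseline does not remove that variation. Nothing here shows bias, invalid inference or a material loss of power.

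The event rate, spread, effect, seated share and Part A to Part B correlation are all assumed, as is the participant as the GEE cluster, which the SAP does not name. Randomization within person is inferred from the micro-randomized wording, the SAP's sent or not-sent decision points, and 80 being half of 160. The Part B sentence in Protocol section 7 could be read alone as randomizing people. In that case stable differences would not cancel and these sizes would not apply. No calculation was made for the sedentary-time model. The gain there should also be small, and close to nil if the mixed model has a participant random intercept, which the SAP does not state.

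**What to change.** Before Part B outcomes are examined, add to SAP PART B:
- From the weeks 1-4 activPAL records within 9AM-5PM, compute for each participant the proportion of seated time points followed by leaving sitting within 5 minutes, and likewise within 30 minutes. Enter the logit of the matching proportion as a covariate in each GEE.
- In the sedentary-time model, enter the participant's mean Part A seated minutes for the matching window.
- State that the reported odds ratio is conditional on this baseline.
- Use the group mean for a participant without usable Part A wear.

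Age, race and gender may stay. The cost is a small set of derived variables and a few SAP sentences, with no new data. The downsides are a slightly different interpretation of the odds ratio and the group-mean substitution. The covariate should be prespecified, because adding it after results are known would look selective.
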